Based on our prior research, comprehensive strategies are urgently needed to improve prediabetes care. Using these findings, we have designed and plan to implement a diabetes prevention clinical pathway which seeks to address some of these common clinician and patient barriers.

Study Objectives

Objective: Our primary objective to design and pilot test the diabetes prevention clinical pathway at a primary care clinic compared to a control primary care clinic.

Study Design

Overview: This is a non-randomized, quasi-experimental intervention study with one comparison group. Eligible patients include those on the prediabetes registry who are seen in the control and intervention clinics during the study period. Data is collected on eligible patients during the baseline (pre-implementation) period and prospectively during the 12-month implementation period.

Intervention Study Population Inclusion/Exclusion:

- Adults age 18 and older, on prediabetes registry, last A1c<6.5%
- Complete one visit (video or office visit) with PCP during intervention period

Blinding

While this study meets the NIH definition of a clinical trial, participants are not randomized or assigned at the patient level. The intervention is implemented clinic-wide and is intended to augment routine care (quality improvement). Therefore, the traditional terms of blinding in a clinical trial are not applicable.

Risks and Benefits

[figure not shown]
We believe the intervention involves minimal medical risk and is aligned with routine, evidence-based care. Participants may benefit from the intervention because of improved follow-up care (including visits, labs, and referrals) which may in turn result in a decreased risk of progression to diabetes. We aim to fill an important gap in knowledge about successful primary care clinic interventions to improve diabetes prevention. We hope to address the public health burden of diabetes by focusing on and improving the primary prevention of diabetes. We believe that the risks to subjects are low and reasonable given the anticipated benefits.

Withdrawal of Subjects

The intervention is intended to improve and augment routine care. Since it is implemented clinic-wide, patients will not have the option to opt out of the intervention. Furthermore, there is no outcome of treatment failure since we are not assigning patients to a particular treatment. They will receive treatments based on individual discussions with their doctor.

Study Procedures

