This is a pre-/post-evaluation of a diabetes prevention clinical pathway that will be implemented over a 12-month period at the intervention clinic. Eligible patients include those on the prediabetes registry who are seen in the control and intervention clinics during the study period. Their first visit with the PCP will be considered V0 (initial data collection) and data will be collected retrospectively (12 months prior to V0) and prospectively at that visit and subsequent primary care visits (V1, V2, V3, etc.) during the 12-month intervention period (see Figure).

The diabetes prevention clinical pathway will focus on the following steps: 1) Screen/test-testing of eligible patients for prediabetes/diabetes, 2) Education- PCPs will be encouraged to take an online learning module and in-person group training on prediabetes management, and patients with prediabetes will receive a handout about prediabetes prior to their upcoming PCP visit, 3) Action- PCPs will use a shared decision-making guide and treatment algorithm to discuss options with patients at their visit, 4) Referral- patients may be referred to DPPs and/or medical nutrition therapy (MNT), and 5) Treat- patients will be scheduled for a follow-up visit within 3-9 months with their PCP or care team (NP) to continue addressing prediabetes.

Group 1 Intervention clinic patients

PCPs in the intervention clinic will be invited and encouraged to attend the 1-hour clinician training session at the beginning of the intervention. This is considered continuing medical education, and we may be able to provide continuing medical education credit for their attendance. The training session will include information on prediabetes treatment guidelines, use of EPIC clinical decision support tools and use of the patient handout to discuss treatment options. There will be interactive skills practice incorporated. This training session may occur on up to 2 occasions to capture all PCPs. We may also record the training session so that PCPs who could not attend can view it later asynchronously.

Patients with prediabetes (e.g., “active” on prediabetes registry) presenting for a routine visit in the intervention clinic will be identified using an EPIC workbench report run the week prior to their upcoming visit. These patients, presenting for in-person or video visits, will receive the handout as an attachment either via MyChart or via email sent from REDCap.

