Enrolled participants will be monitored throughout the study for untoward incidents (e.g., “Adverse Events”) occurring during the study. The Principal Investigator (and other designated individuals, if necessary) will conduct regular monitoring for safety concerns and provide general oversight for human subject safety requirements. Where necessary these occurrences will be evaluated for severity, attribution, and possible trends. All adverse events that are anticipated or described in the informed consent form will be logged appropriately and reported to the IRB on at least an annual basis (e.g., at continuing review).

Any Unanticipated Problems or unexpected “Serious Adverse Events” *related* to the study intervention or affecting the risk/benefit profile of the study, will be reported to the IRB promptly, and, in all cases, within 10 business days of discovery. Unplanned and non-emergent deviations from the IRB approved protocol will be logged and reported to the IRB annually at continuing review; all planned deviations will be submitted as a Change in Research to the IRB for approval and prior to implementation. All other event reporting requirements will be followed and all necessary parties will be notified of events/problems encountered in the study and/or changes in research, in accordance with all applicable regulations and guidelines.

Statistical Plan

Sample Size Determination and Power

We estimate that 1200 patients with prediabetes will be seen over the 12-month intervention period within each clinic (total sample of 2400 patients). Based on this sample, we estimate we will have 100% power to detect a change in rate of referral to DPPs from 0% to 25%. Additionally, we estimate that we will have 100% power to detect a change in documented prediabetes diagnosis from 10% (baseline rate estimated from Johns Hopkins data) to 34% (national estimate of the prevalence of prediabetes), follow-up lab testing completed from 50% (baseline rate estimated from Johns Hopkins data) to 60%, and referral to nutrition from 1% (baseline rate estimated from Johns Hopkins data) to 10%. In our analysis, we will assess the differences in trend of the outcomes in the baseline, intensive implementation, and sustainment periods.

Primary outcome variable

The primary outcome is whether patients with prediabetes are referred to a DPP and/or medical nutrition therapy and/or start metformin.

Secondary outcome variables

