The secondary outcomes are whether patients: 1) enroll in the DPP, 2) attend a medical nutrition therapy visit, 3) complete follow-up glycemic testing, 4) fill metformin, 5) achieve weight loss $\geq 5\%$ and 6) complete PCP/team follow-up visit.

Other process outcomes we will look at include whether MyChart messages with the prediabetes handout are read.

Statistical Methods

For the analysis, we will include patients with prediabetes (identified by prediabetes registry) who have completed at least once PCP visit during the first 6 months of the 12-month intervention period. We will compare the primary outcomes and other secondary outcomes between the intervention and control clinics.

We will conduct an interrupted time series analysis to evaluate the differences in trend of the outcomes in the baseline (V0-12m), intensive implementation (T0-T6m), and sustainment periods (T6m-T12m) at the patient level. We will compare these outcomes in the pre- and post-intervention periods using logistic regression models with generalized estimating equations to account for repeated observations within patients. We will use multivariate logistic regression models to determine predictors of these outcomes adjusting for race, age, and baseline HbA1c. We may adjust for clinic-level characteristics, such as patient safety culture using GLINT survey data from 2021 and 2022 if available. We will only request aggregate data from the clinic-level on safety culture.

Study Administration

Funding Source

Funding for this study is provided by the National Institute of Diabetes and Digestive Kidney Diseases under Award Number K23DK118205 (PI: [name]).

Subject Stipends and Payments

Patients who complete the survey will receive a \$10 gift card, either mailed to their home address or sent as an e-gift card based on patient preference. The last survey question will ask them to provide this information, which will not be linked to other responses. Clinicians who

complete the survey will get a \$25 e-gift card sent to the email address they provide. Again, their response to this question will not be linked to other responses.

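### A 12-month baseline tied to each patient's first visit is set against two 6-month periods on a T0 clock, so patient-level pre/post estimates can be biased with no true effect

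*Combined protocol and SAP*

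**What the plan says.** Study Procedures anchors the baseline on the patient: "Their first visit with the PCP will be considered V0 (initial data collection) and data will be collected retrospectively (12 months prior to V0"). Follow-up data are then collected "prospectively at that visit and subsequent primary care visits (V1, V2, V3, etc.) during the 12-month intervention period (see Figure"). I read V0 as the first PCP visit in the intervention period. The Overview under Study Design describes the same baseline as falling before implementation: "Data is collected on eligible patients during the baseline (pre-implementation) period and prospectively during the 12-month implementation period".

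Statistical Methods restricts the analysis to registry patients who "completed at least once PCP visit during the first 6 months of the 12-month intervention period". It then plans an interrupted time series over "the baseline (V0-12m), intensive implementation (T0-T6m), and sustainment periods (T6m-T12m) at the patient level".

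The two comparisons stand in separate sentences. One reads "We will compare the primary outcomes and other secondary outcomes between the intervention and control clinics". The other reads "We will compare these outcomes in the pre- and post-intervention periods using logistic regression models with generalized estimating equations", the GEE being there to handle repeated observations on a patient. The named covariates are race, age and baseline HbA1c, with clinic safety culture as an option. The plan gives no clinic-by-period term, scoring interval, person-time term or definition of the repeated observation.

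**The concern.** The baseline runs on the patient's clock for 12 months. The later periods run on a T0 clock for 6 months each.

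- **If T0 is launch**, the months from launch to V0 contain no PCP visit by construction. They count as baseline although they follow launch, and they also lie inside T0-T6m.
- **If T0 is V0**, sustainment is cut short when the 12-month intervention period ends.
- **In both cases**, the first post-launch period is guaranteed a visit and the baseline is not.

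With no true effect, a within-clinic estimate could therefore show a fall or a rise, depending on a scoring choice the plan leaves open. A real sustained gain could also read as no change. Pre/post change is prominent here: Study Procedures calls the study a pre/post evaluation, and the power statement is framed as changes in rates.

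**Working it through.** **The plan's own figure.** Sample Size Determination and Power claims 100% power with 1200 patients per clinic. A two-proportion calculation at an assumed two-sided 0.05 gives 100% for 0% to 25%, 100% for 10% to 34%, 99.86% for 50% to 60%, and 100% for 1% to 10%. The claim reproduces, but for a simple two-proportion change and not for a clinic-by-period contrast.

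**Null model (assumptions, not in the documents).** Visits are Poisson at 1, 1.5, 2 or 3 a year. Each PCP visit carries a 5% event chance, and events occur only at visits. V0 is the first visit after launch, entry needs a visit in months 0-6, T0 is launch, and there is no effect.

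**By hand at 2 visits a year:**

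- Sustainment, 6 months: 1 - exp(-2 x 0.5 x 0.05) = 0.0488, odds 0.0513.
- T0-T6m, given at least one visit: 0.0488 / (1 - exp(-1)) = 0.0488 / 0.632 = 0.0772, odds 0.0836.
- Baseline: mean V0 is month 2.51, so visits can occur in only 12 - 2.51 = 9.49 of the 12 months. 1 - exp(-2 x (9.49/12) x 0.05) = 0.0760, odds 0.0823.
- One score per period: sustainment OR = 0.0513 / 0.0823 = 0.62; T0-T6m OR = 0.0836 / 0.0823 = 1.02.
- Monthly scoring: sustainment ratio is about 12 / 9.49 = 1.26. For T0-T6m, 1 / 0.632 = 1.58 visits in 6 months stand against 2 x 9.49/12 = 1.58 in 12 months, a ratio of 2.0.
- Equal calendar windows: the 6 months before launch also give 0.0488, so sustainment OR = 1.00 and T0-T6m OR = 0.0836 / 0.0513 = 1.63.

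**Simulation, 1,000,000 patients per rate before selection (null OR):**

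| Visits per year | 1 | 1.5 | 2 | 3 |
|---|---|---|---|---|
| One score per period, sustainment | 0.64 | 0.64 | 0.62 | 0.61 |
| One score per period, T0-T6m | 1.70 | 1.24 | 1.01 | 0.80 |
| Monthly, sustainment | 1.32 | 1.29 | 1.25 | 1.24 |
| Monthly, T0-T6m | 3.35 | 2.45 | 2.00 | 1.60 |
| 12 months post against V0 baseline | 2.38 | 1.93 | 1.69 | 1.47 |
| T0 = V0, first 6 months | 2.01 | 1.54 | 1.29 | 1.04 |
| T0 = V0, truncated sustainment | 0.34 | 0.35 | 0.36 | 0.37 |
| Equal calendar windows, T0-T6m | 2.65 | 1.96 | 1.62 | 1.32 |

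With equal calendar windows, sustainment is 0.99-1.01 at every rate. With event chances of 1% to 20%, the one-score sustainment OR spans 0.56-0.68. Under monthly scoring the baseline also acquires a false downward slope, OR 0.90-0.92 per month.

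**Visit as the unit.** The same model gives ORs of 0.97 to 1.02 in both periods, so no bias.

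**A real effect.** If the event chance per visit rises 1.5-fold after launch, the sustainment OR is about 0.9 to 1.0 with one score per period, and about 1.5 with equal windows.

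**Between clinics.** The ratio of null ORs, one score per period, is 0.95-1.06 for sustainment over all pairs of rates within 1-3 a year. For T0-T6m it is 1.00 at equal rates, 0.82 at 2 against 1.5 visits, 0.79 at 3 against 2, and 0.47-2.13 over all pairs.

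**Check that does not tie events to visits.** With a constant rate, p6 = 1 - sqrt(1 - p12). The sponsor's 12-month rates in Purpose of the Study Protocol then give:

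- repeat testing 63.4% to 39.5%, OR 0.38;
- metformin 5.4% to 2.7%, OR 0.49;
- nutrition referral 1.0% to 0.5%, OR 0.50.

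The power section's "follow-up lab testing completed from 50% (baseline rate estimated from Johns Hopkins data) to 60"%, with its 50% taken as a 12-month rate, gives 29.3%, OR 0.41. Nothing can be computed for the primary composite, because the documents hold no measured DPP referral rate.

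**The case against.** The strongest reply is that the visit may be the unit. Data are collected visit by visit and the GEE is there for repeated observations within patients. On that reading the artefact vanishes under the model above. The patient-level wording weighs against it but does not exclude it. This stands, and it makes the point conditional.

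Four further replies carry weight:

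- **The figure.** It may define T0. A definition alone would not cure the problem: with T0 = V0 the guaranteed visit and unequal windows remain.
- **The control clinic.** A between-clinic comparison is stated, and the artefact mostly cancels there for sustainment. This stands, but the plan does not tie that comparison to the pre/post model.
- **The assumptions.** Visit rates and event chances are assumed. The monthly-scoring rise needs events confined to PCP visits and disappears under a constant rate; the one-score fall survives under both models. With one score per period, T0-T6m is near null at about 2 visits a year. The planned effects are mostly far larger than 1.5-fold, though 50% to 60% testing is modest.
- **The remedy.** Equal windows move the one-score T0-T6m OR further from 1 at every rate, from 1.70-0.80 to 2.65-1.32. That is correct: the entry-visit rule drives this period more than the clock does.

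**Conclusion.** The concern holds conditionally. On patient-level scoring, by period or by month, the windows as written can give wrong within-clinic pre/post estimates under no effect. The sustainment OR is about 0.60-0.65 or 1.2-1.3 according to the scoring. T0-T6m can err in either direction with one score per period. The sizes rest on the assumed 1-3 visits a year, 5% event chance at PCP visits only, and T0 at launch.

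A reader might infer three stronger things that the documents do not support:

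- **That the estimates are biased whatever the coding.** They are not if the visit is the unit, and the plan does not name the unit.
- **That the missing clinic-by-period term causes the bias.** It leaves the bias uncorrected. The causes are the windows and the entry visit.
- **That the comparison of clinics is lost.** It is largely protected for sustainment; for T0-T6m it depends on similar visit rates. With one clinic per arm, it still cannot separate clinic differences from the effect.

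This should be fixed before analysis. Confidence is medium.

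**What to change.** 1. State T0, its relation to V0, and a common launch date for both clinics. State the GEE observation unit.
2. For patient-level scoring, put both clinics on one calendar axis with equal intervals (T-12m to T-6m, T-6m to T0, T0 to T6m, T6m to T12m, or months). Score each yes/no outcome once per interval and count no post-launch time as baseline.
3. Make the clinic-by-period interaction in the logistic GEE the tested effect. Report within-clinic changes as descriptive only.
4. Read T0-T6m only through the between-clinic contrast, and report visits per patient by clinic and period beside it. Equal windows repair within-clinic sustainment but not this period.

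**Cost.** SAP wording, plus a record look-back to T0-12m. For a patient entering at month 6 that is 6 + 12 = 18 months before V0, beyond the 12 in Study Procedures. Under the Safety and Adverse Events section, a planned departure of this kind goes to the IRB as a Change in Research. No new data are collected from patients.

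**Power.** For the contrast, SE² = [p1q1 + p2q2 - 2r√(p1q1p2q2) + 2p1q1(1 - r)] / n, with q = 1 - p, r the within-patient correlation, and the control clinic flat at p1. For testing at 50% to 60%, n = 1200 and r = 0, SE² = (0.25 + 0.24 + 0.50)/1200 = 0.000825, giving 93.6% power (97.3% at r = 0.2, 99.9% at r = 0.5). If only an assumed 600 per clinic meet the 6-month visit rule, power is 69.2%, 78.6% and 93.6%. The other three planned changes stay at 100% with 1200 per clinic.

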**Implementation and Evaluation of a Diabetes Prevention
Clinical Pathway in Primary Care**

NCT05265312

Date: 7/11/2023

Introduction

Abstract and Background:

Prediabetes is a significant public health problem affecting 88 million U.S. adults. Evidence suggests that the vast majority of people with prediabetes are unaware that they have this condition and many are not receiving appropriate care for prediabetes, including referral to evidence-based programs like the Diabetes Prevention Programs. In our retrospective cohort study of patients with prediabetes from Johns Hopkins Health Systems, we found that the rates of prediabetes clinical care activities are low. In our qualitative studies, we found that primary care physician (PCP) barriers include low knowledge about Diabetes Prevention Programs and misperceptions of insurance coverage of these programs and inadequate clinical staff to address prediabetes. Common patient barriers to taking action to prevent diabetes include lack of motivation, time and resources.

Primary Hypothesis: We hypothesize that the clinical pathway will result in increased clinician screening and intervention and improve patient engagement in diabetes prevention. We will compare results from the intervention clinic compared to a control clinic. If successful, we plan to implement and test the effectiveness of this clinical pathway across the entire health system.

Purpose of the Study Protocol: As described above, we have conducted several studies to understand current practices in prediabetes care across the Johns Hopkins Health Systems. In our retrospective cohort study of patients with prediabetes from Johns Hopkins, we found that the rates of prediabetes clinical care activities are low. Within 12 months, 63.4% had repeat glycemic testing, yet only 10.4% had coded diagnoses of prediabetes, 1.0% were referred for nutrition services, and 5.4% were prescribed metformin. We were unable to evaluate uptake of Diabetes Prevention Programs (DPPs) since a referral order was not in place until recently. In our qualitative studies, we found that clinician barriers include low knowledge about DPPs and misperceptions of insurance coverage of these programs and inadequate clinical staff to address prediabetes. Common patient barriers to taking action to prevent diabetes include lack of motivation, time and resources.

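### The pre/post analysis sets a 12-month baseline against 6-month periods for cumulative yes/no outcomes, with no exposure adjustment or clinic-by-period term, which biases the within-clinic contrast downward

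*Combined protocol and SAP*

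**What the plan says.** Statistical Methods describes an interrupted time series at the patient level over three periods: "baseline (V0-12m), intensive implementation (T0-T6m), and sustainment periods (T6m-T12m". Study Procedures confirms the length of the baseline: "data will be collected retrospectively (12 months prior to V0". The next modelling sentence reads "We will compare these outcomes in the pre- and post-intervention periods using logistic regression models with generalized estimating equations", with GEE used to handle repeated observations on the same patient. No offset, time unit or period-length term is given, and no clinic-by-period term is written. A comparison of the intervention and control clinics is stated separately, just before.

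The analysis set is patients "who have completed at least once PCP visit during the first 6 months of the 12-month intervention period". Data after V0 are collected "prospectively at that visit and subsequent primary care visits (V1, V2, V3, etc.) during the 12-month intervention period".

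Follow-up testing is listed under Secondary outcome variables as "3) complete follow-up glycemic testing", with no window. Sample Size Determination and Power plans on "follow-up lab testing completed from 50% (baseline rate estimated from Johns Hopkins data) to 60" percent, again with no window. The only testing rate with a window is in the Introduction, under Purpose of the Study Protocol: "Within 12 months, 63.4% had repeat glycemic testing". Both baseline figures are attributed to Johns Hopkins data, and the document does not reconcile them.

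**The concern.** The proportion of patients tested at least once can only rise as the window lengthens. A 12-month baseline therefore has a head start over a 6-month follow-up period, and a logistic model that treats the two as like for like reads the shorter window as a lower rate. Pooling the two post periods does not restore balance if post data are counted from V0 and stop at month 12. Patients entering up to month 6 then have only 6 to 12 months of follow-up.

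At stake is the within-clinic pre/post estimate. It could hide a real improvement in testing or, on one reading of the model, show it as a fall. The same periods apply to the other cumulative yes/no outcomes, including the primary composite. The documents give no baseline rate or target for that composite, so the size is worked out here for testing only.

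**Working it through.** **Inputs.** Baseline 12 months, post periods 6 months each (Statistical Methods, Study Procedures). Planned testing 50% to 60%, 1200 patients per clinic (Sample Size). Repeat testing 63.4% within 12 months (Introduction); the same 10-point gain gives 73.4%. Assumptions: all four are 12-month rates, testing occurs at a constant rate, and each patient contributes one yes/no per period.

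**The plan's own figure.** For 50% against 60% at 1200 per clinic, two-sided 0.05 (alpha is not stated), the pooled-variance normal approximation gives power = Φ[(0.10 − 1.96 × √(2 × 0.55 × 0.45/1200)) / √((0.25 + 0.24)/1200)] = 99.9%. The stated 100% is reproduced for a simple two-group comparison.

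**Conversion.** Rate in t months = 1 − (1 − p)^(t/12), where p is the 12-month rate. At 6 months this is 1 − √(1 − p).

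| 12-month rate | 6-month rate |
|---|---|
| 50% | 29.3% |
| 60% | 36.8% |
| 63.4% | 39.5% |
| 73.4% | 48.4% |

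**12 months before against 6 months after, planned gain present.**
- 50% reads as 36.8%: −13.2 points, odds ratio 0.58. Equal 12-month windows give 1.50; equal 6-month windows (29.3% to 36.8%) give 1.40.
- 63.4% reads as 48.4%: −15.0 points, odds ratio 0.54. Equal 12-month windows give 1.59.
- From a 50% baseline, the true 12-month rate would have to reach 1 − 0.5² = 75% to show no change.

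**12 months before against all follow-up to month 12.** With even entry over months 0–6, average the conversion over t = 6 to 12. With λ = −ln(1 − p)/12, the mean is 1 − (e^(−6λ) − e^(−12λ))/(6λ).
- p = 60%: 1 − (0.632 − 0.400)/0.458 = 49.3%, against 50% (odds ratio 0.97).
- p = 73.4%: 1 − (0.516 − 0.266)/0.662 = 62.3%, against 63.4% (odds ratio 0.95).

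**Without the constant-rate assumption.** At 12 versus 6 months the sign is right only if the share of 12-month testers who are tested in the first 6 months exceeds 50/60 = 83%, or 63.4/73.4 = 86%.

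**What the control clinic does.** With no true change, its 50% reads as 29.3% (−20.7 points, odds ratio 0.41). The difference between clinics is −13.2 − (−20.7) = +7.5 points, and the ratio of odds ratios is 0.581/0.414 = 1.40, the equal 6-month value. An interaction term therefore removes the artefact in this case.

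**Power for that interaction on equal 6-month windows.** Wald test, two-sided 0.05, control clinic unchanged, patients independent within clinic. Effect: ln 1.403 = 0.339 (29.3% to 36.8%) or ln 1.438 = 0.363 (39.5% to 48.4%). The variance in each clinic is [1/(p₀q₀) + 1/(p₁q₁) − 2ρ/√(p₀q₀p₁q₁)]/n, where p₀ and p₁ are the pre and post rates, q = 1 − p, and ρ is the within-patient correlation. The two clinics are summed. The number seen in the first 6 months is not given, so n is a range.

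| n per clinic (assumed) | ρ = 0 | ρ = 0.3 |
|---|---|---|
| 600 | 48–59% | 63–74% |
| 900 | 65–76% | 80–89% |
| 1200 | 77–87% | 90–96% |

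Unrounded rates are used; rounding them to one decimal moves the 77% to 78%.

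**The case against.** The strongest reply is that the plan never says each patient contributes one yes/no per period. It speaks of trends within periods and of repeated observations, and a trend needs more than one point per period. If the units were months, the windows would be equal and the artefact would not arise. That stands as a limit. However, no unit is stated, and the only divisions of time named are the three unequal ones.

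A reader might infer that the trial would report the pathway as lowering testing. The documents do not support that without conditions. The hypothesis and objective compare two clinics, and that comparison within a period is untouched. The wrong sign needs the baseline set against a single 6-month period. The GEE sentence speaks of pre and post periods, and on the pooled reading the gain is lost rather than materially reversed. If records ran a full 12 months from each V0, even that would not happen.

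Testing may also cluster around V0, because every patient has a PCP visit then. This would push the other way. It is not quantified beyond the 83% and 86% break-even shares, and clustering in the first period would make sustainment look worse.

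A reader might also infer that the baseline overlaps the implementation period for patients first seen late. This depends on what T0 means. Study Procedures refers to a figure that is not shown, so it cannot be counted as a fault. Nor is the stated 100% power an arithmetical error; it answers a simpler question than the interaction.

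**Conclusion.** The point holds for the within-clinic pre/post contrast. Followed as written, with one value per patient per period, the plan compares cumulative outcomes over unequal windows with nothing in the model to correct for it, and the bias is downward. For follow-up testing the planned 10-point gain would read as a fall of 13.2 points (50% baseline) or 15.0 points (63.4% baseline) at 12 versus 6 months, and as roughly no change if the post period is pooled to month 12. These sizes rest on a constant testing rate, on 50% and 60% being 12-month figures and, for the pooled case, on even entry with follow-up ending at month 12. The direction at 12 versus 6 months needs only that no more than about 83% to 86% of 12-month testers are tested in the first 6. The between-clinic comparison is unaffected, a clinic-by-period term would largely cancel the artefact, and equal short units would avoid it. This is a weakness to correct before analysis; it does not undermine every planned result.

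**What to change.** **Statistical Methods and Secondary outcome variables.** Define each cumulative outcome over windows of equal length before and after V0. One example is 6-month windows at −12 to −6, −6 to 0, 0 to 6, and 6 to 12 months where records are complete. Alternatively, state that equal monthly units are used. Say which window holds tests done on the day of V0. Fit one GEE model with clinic, period and clinic-by-period terms, and name the interaction as the effect.

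Before settling the window length, note that Study Procedures gives the follow-up visit as 3–9 months in the pathway steps and 3–6 months under Group 1. The two should be reconciled, since a 6-month window cuts across the former.

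**Sample Size Determination and Power.** State the source and window of the 50% and 60%, reconcile the 50% with the 63.4%, and restate power for the interaction on the actual analysis set, using the planned gain converted to the chosen window (7.5 to 8.9 points over 6 months under the assumptions above, not 10).

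**Cost.** Small: rewording, and a stated power less favourable than 100%. The first three example windows use data already planned for every patient in the analysis set. Only the 6 to 12 month window may need a longer record extract. Enrolment does not change.
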